## 1.2 **Rationale**

This study involves efforts to advance the science of prevention in early childhood mental health in low-resource communities. We will investigate the effectiveness, practical implementation strategies, and underlying mechanisms of the *PD* in urban and rural Uganda. We will compare effectiveness of two *PD* implementation approaches (with and without T-Wellness) using a hybrid effectiveness-implementation CRCT. **Figure 3** shows the conceptual model for *PD* and *PDT* Theory of change in LMIC contexts, which considers *intermediate intervention effectiveness outcomes* (teacher EBI practice) and *distal effectiveness outcomes* (including primary child mental health outcomes and secondary child behavioral outcomes, defined in Table 2). *PD* is expected to change teachers' EBI practices; and the impact of *PD* on distal child mental health outcomes will be mediated primarily through changes in teachers' practice of EBI strategies. Similarly, we expect that *PDT (PD+T-Wellness)* will also have impact on distal child mental health outcomes, and this will be mediated primarily through improvement in both teachers' EBI practices/behaviors and teachers' stress management skills (cognitive and behavioral control/ coping of stress). We anticipate *changes in child behaviors will be observed in the secondary outcome domains before the mental health outcomes* (primary distal outcomes). Because *PD/PDT* will be implemented in diverse contexts, our theory of change also considers moderators from aspects of the Consolidated Framework for Implementation Research (CFIR), which proposes that five domains of contextual factors can impact effectiveness-implementation. Specifically, we expect that certain *individual, intervention implementation, and school contexts* may also influence (or moderate) intervention effectiveness. We consider geographic region (urban/ rural) as the primary moderator, and other CFIR factors listed in the figure as secondary moderators. This theory of change has been partially tested (constructs in 'red' in Figure 3) and supported in previous *PD* studies. This study will formally examine the cost-effectiveness and test the *PD/PTD* theory of change with a larger diverse sample and using scalable approaches. We select a foreign low-resource country as our study site because it provides an ideal setting to test how a mental health system can be strengthened through careful consideration of strategies while simultaneously examining effectiveness outcomes of an EBI. Also, Ugandan context is similar to other underserved and under-resourced communities in the US and other LMICs. Therefore, knowledge generated from our study will be relevant globally.

**Figure 3. Hypothesized Mechanisms for PD & PDT impact on Teachers and Children**

## INNOVATION

The project is innovative in its scale, methods, scientific contribution, and structure. **1)** We have brought together a team of international experts in policy, intervention content development, large-scale program implementation, biostatistics, and health economics to launch the largest population-based early childhood mental health prevention trial in low-resource African contexts paired with a comprehensive plan to support MOH, MOE, and TTC to set up a sustainable school-based preventive mental health training and service structure. **2)** Studying effectiveness and theory of change of a population-based mental health preventive intervention in Ugandan and US context simultaneously is innovative. In partnership with public stakeholders, *PD* is currently being tested in the US context (also led by this investigation team, but with separate funding sources). The support from NIH of this *PD* scale-up effort in Uganda will provide a unique opportunity to study effectiveness as well as to compare underlying mechanisms across two countries. Lessons learned from this effectiveness and theory of change testing will inform generalizability of intervention and theory across contexts, as well as facilitate new innovations to address similar mental health disparities in countries with similar adversity and resource barriers globally. **3)** Our localized scalable implementation models (for urban and rural Uganda) and teacher task-shifting preventive service model is innovative in LMIC contexts. Our scalable approaches integrate MOH and MOE policy efforts and consider a localized multi-stakeholder task-shifting/ task-sharing collaborative approach. This approach ensures local fit and adaptability of implementation systems to support EBIs in diverse contexts. Furthermore, by training teachers to apply mental health promotion EBI strategies in daily practice, it has the potential to not only promote children's mental health, but also to strengthen school mental health systems and service (e.g., increase workforce, EBI knowledge sharing from teachers to other community members). Our approach also lays out a service model for WHO's *Action Plan and Service Pyramid* frameworks, which suggest providing accessible population-based child mental health preventive intervention in schools. **4)** Studying workforce/teacher stress management strategies and underlying mechanisms using the MOST design in the context of effectiveness RCT is innovative. Our study addresses a critical CHW workforce stress/job burden issue that has been frequently reported in LMICs. Applying the pragmatic MOST design increases research efficiency, provides an opportunity to further optimize EBIs, and ensures expected T-Wellness impact before conducting the cRCT. Our study contributes to new knowledge and new solutions that may overcome workforce stress, which may also maximize EBI uptake, effectiveness, and sustainability. Findings will also inform policy decisions in EBI programming and workforce development. **5)** Our design integrating multiple implementation science frameworks is innovative. We integrate several recently developed conceptual models from scale-up and implementation science. This provides a new way to synthesize conceptual models that is more in line with complex real-world large-sale intervention implementation. Evidence from our research can inform new integrated frameworks to guide scaling-up research and better understand practice relevant behavioral change processes.

### 1.3 Potential Risks & Benefits

#### 1.3.1 Known Potential Risks

There are no known physical risks associated with the study. However, there is the possibility that teachers, principals, PTAs, parents or students will experience some inconvenience, embarrassment, or distress while completing the interviews/questionnaires or when being observed. In addition, because teacher recruitment and intervention program implementation will be carried out in a group format (including Pre-primary to Primary 1-4 grade teachers from study schools), it is not feasible to guarantee complete confidentiality to teachers who decline to participate, as other participating teachers may notice teachers who are not present in the training. Furthermore, adult participants will be made aware of the limits to confidentiality, especially in adhering to legal status regarding reporting to child protection agencies information if study children are found to be at-risk for abuse or neglect or are being abused or neglected. To minimize these risks, we have developed plans to protect research participants through consents, preventive actions, and risk mitigation.

### 1.3.2 Known Potential Benefits

The training of the TTC faculty, school teachers and PTAs can strengthen local child mental health preventive service capacity. Teachers/PTAs/TTC staff who participate in PD/PDT may develop new knowledge and skills that are useful to promote their children/students' mental health. They may also benefit from the support of professionals and their colleagues. In addition, parents and children of the participated schools will benefit from their teachers. Teachers/PTAs may improve skills in promoting parent involvement and child social emotional and mental health. The minor risks of participation are considered reasonable in relation to the anticipated benefits to subjects and the knowledge that may result from this study.

## 2 Objectives and Purpose

### **Aim 1. To evaluate the short- and longer-term effectiveness of PD and PDT.**

Hypotheses: (a) PD, implemented using localized scalable approaches, is more effective than control; and (b) PDT is more effective for CHWs/teachers than PD alone; and (c) PDT has a more favorable cost-effectiveness ratio than PD alone.

### **Aim 2. To examine effectiveness mechanisms and theory of change underlying the EBIs.**

Hypotheses: the mediational mechanisms of PD (teacher EBI strategy use as a mediator between intervention and child outcomes) and PDT (teacher stress management and EBI strategy use as mediators) will be supported.

### **Aim 3. To examine implementation contextual factors and mechanisms that contribute to CHWs' (teachers') uptake and sustainment of EBI strategies within PD and PDT schools**

#### **2.1 Primary Objective**

The primary teacher effectiveness outcomes (or intermediate effectiveness outcomes) are teachers' EBI strategy use, teacher stress management. The primary child effectiveness outcome is child mental health (externalizing and internalizing problems)

#### **2.2 Secondary Objectives (if applicable)**

The secondary child effectiveness outcomes are three behavioral-cognitive domains: emotion regulation, social relationships (student-teacher & peer relationship), and executive functioning (cognitive system function).

## 3 Study Design and Endpoints

### **3.1 Description of Study Design**

**Study Overview.** We will study the effectiveness and mechanisms of PD/PDT in diverse Ugandan contexts. Year 1 will be the preparation period, in which we will establish localized scalable PD implementation structures in two study regions, and to optimize the T-Wellness by carrying out a user-centered testing study with 4 schools (~60 teachers) (in a 4-6 month time frame in Year 1). In Years 2-4, we will carry out a cRCT to study effectiveness, cost-effectiveness, and underlying mechanisms. Drs. [name] and [name] with expertise in RCTs and quantitative analyses will guide the effectiveness and mechanism analyses. For the cost-effectiveness comparisons, [name] will guide the planning and analyses. [name], with expertise in stress management and qualitative studies, will guide the T-Wellness testing and qualitative analyses.

## 4 Study Enrollment and Withdrawal

### **4.1 Inclusion Criteria**

In order to be eligible to participate in this study, an individual must meet all of the following criteria:

1. The inclusion criteria for the school staff (teachers, head teachers) are: they must be in the recruited study schools and teaching in Pre-Primary to Primary 4 classrooms or holding the head teachers/administration leadership position in school. The inclusion criteria for Parent Leaders are: they must be at least 18 years old and have served as a Parent-Teacher-Association member or Parent Leader in the school for at least 1 year.
2. The inclusion criteria for the PD/PDT program implementers are: they must have current employment with eligible partners (i.e., medical/mental health institutions, Teacher Training Colleges), with professional experiences in teacher training or mental health training.
3. The inclusion criteria for parents are: caregivers must be at least 18 years old, their children must be enrolled in Pre-Primary or Primary 1 to 4 classes (or between 3 to 10 years old) in the recruited schools, and willing to have their child to be assessed by research staff. Parents and children will have diverse characteristics (e.g., randomly selected from school student lists). About 10% families will be randomly selected from the student lists. The proposed study will be open to both men and women caregivers

#### **4.2 Exclusion Criteria**

An individual who meets any of the following criteria will be excluded from participation in this study:

1. Evidence of psychopathology or cognitive impairment severe enough to preclude giving consent, or completing the survey instruments or the focus group of the study.
2. Minors (age <18) will also be excluded. Additional criteria should be included as appropriate for the study design and risk.

#### **4.3 Vulnerable Subjects**

The key intervention targets for this study are teachers, and evaluate whether impacts on teachers will improve child mental health. For schools where the principal agree to participate in the PD/PDT, individual teachers will still have the right to refuse to participate at any time during the study. Research staff will ensure that the school staffs are aware of this during the consent process. To ensure that non-participating teachers are not discriminated against by principals, school personnel, or participating teachers, we have worked with MOE partners and developed several policies, which will be in place from the start of the study. One, we will apply a recruitment approach that will “normalize” the decision not to participate. Specifically, when consenting principals and teachers, we will explicitly explain that the study aims to test a new school approach to help promote students’ health and development, and that we are asking for volunteer schools and teachers to participate and provide their feedback. We will notify principals upfront that teacher participation is completely voluntary and does not reflect on the community or researchers’ views about principals’ leadership or the image of their school and teachers. We will also notify teachers that there are many reasons why some teachers may not participate, including having unique responsibilities (either personal or professional) that other teachers may not have. We will strongly urge school teachers to be respectful of others’ choices to not participate, given a range of possible circumstances. This recruitment approach will likely minimize any potential feelings of discomfort for non-participating teachers, and will minimize potential discrimination toward non-participating teachers.

Although the intervention is not directly targeted on children, and there will be indirect benefit on children (through positive changes on teachers). Because the primary effectiveness outcomes are focusing on children; therefore, we will include children as our study subjects and ask children's own perception of their behaviors and environment. We will obtain parent's permission/consent (which will be documented) and the study child's assent before conducting child assessment. The child assessment will be conducted by trained research staff, and will take about 20-30 minutes. All research staff who conduct child testing/assessment will be trained and equipped with skills to manage children distress. Research staff will also work with the targeted students' teachers to schedule appropriate time for assessments, so it will not interrupt study children's class activities or impact on their right to attend classes. If children have limited capability and cannot reasonably respond to assessment questions, research staff will stop the assessment. The intervention and child assessment are no greater than minimal risk, and the child assessments can help better understand impacts through children's own perspective. This research presents an opportunity to further the understanding children's need and impacts of prevention.

#### **4.4 Strategies for Recruitment and Retention**

The target of the intervention for this proposed project is school staff (i.e., teachers and Parent-Teacher-Association [PTA] members/Parent Leaders). The intervention is at a system-level, which is to train school staff to provide preventive intervention to students and parents. Subjects for the teacher and children's effectiveness outcomes will be reported by teachers, parents, and students. Objective observation (by trained study staff) on teachers' EBI practice in classrooms will also be conducted.

##### **Recruitment and Referral Sources:**

- Intervention Implementer/ Trainer: Drs. [name] and [name] We will work with TTC and, MOE, and MOH to finalize the referral and recruitment process. Trainers will be identified and invited to participate. Participation will be completely voluntary, with no consequence for opting out of participation due to personal reasons.
- Schools: We will work with Ministry of Education (MOE) to finalize the referral and recruitment procedure. In general, public primary schools in targeted districts will be identified from governmental school lists in two study districts (urban and rural) provided by MOE. Principals of these schools will be invited to attend one of the information sessions hosted by the Ugandan intervention implementation team. During the recruitment session, principals will be provided with details of study requirements and intervention. They will have an opportunity to ask questions and also complete a questionnaire that seeks to gather information on school demographics, commitment to remain in a randomized condition, willingness to facilitate data collection, and allocate staff time to participate in the study. Eligible schools will be selected based on school leaders' and principals' expressed of interest and their agreement to allow teachers' voluntary participation. To ensure approximately similar characteristics in the intervention and control conditions, a statistician, unfamiliar with study schools, will match schools on size (i.e., number of teachers and students), location (urban/rural), and quality/performance from the eligible school list. A stratified-block randomization design will be applied. We will work with MOE to finalize a systematic approach to select the final 36 schools.

• **Teachers and PTA Members:** For the selected 36 schools, all pre-primary and Primary 1 to 4 teachers, serving students between 3 and 10 years old will be eligible to participate. Teachers' participation will be completely voluntary, with no consequence for opting out of participation due to personal reasons (see human subjects section for detail about teacher protection). PTA members from 24 intervention schools will be recruited to participate. For schools that do not have a PTA, Parent Leaders will be recruited. PTA members and Parent Leaders that are actively involved and have at least a year of experience in working with schools will be eligible. We will work with the intervention school to plan for recruitment and training of one PTA member from each intervention school (control schools will not have an identified PTA members). We anticipate that 540 teachers from 36 schools will participate in the evaluation study; and 360 intervention school teachers will be participated in intervention.

• **Families (Parent & child pairs):** Ugandan primary schools have on average about 550 students. Given the large numbers of students in schools, research staff will randomly select 10% of students and families from each school based on student lists provided by teachers (using random number generator software). Teachers will be informed of the students randomly selected for participation in the assessments and asked to introduce the study to the selected parents or primary caregivers. Targeted parents will be invited to consent for interviews, for teachers to complete ratings on their child's behavior, and for research staff to carry out objective assessments with their child.

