Population	The study populations include: (1) Teachers for the T-Wellness User-centered & Optimization testing (n=60; from 4 non-RCT schools in year 1); (2) Intervention implementers (n=8; 6 TTC trainers and 2 mental health professionals from urban/Kampala and rural/Hoima regions; (3) Primary school teachers/head teachers (n=540) from 36 schools and PTA leaders (n=24) from 24 intervention schools; and (4) Children and caregivers (n= 1980 parent-child pairs) from 36 study schools.
Study Sites	36 schools (12 receiving PD, 12 receive PDT, and 12 control).
Number of participants	2544 adults and 1980 children for Aims 1-3 (This is not including 60 teachers for the T-Wellness User-centered testing during Year 1 preparation year).

[figure not shown]

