Description of Study Intervention/Procedure	

• Prior to the RCT study (or during Year 1), T-Wellness Package (a brief teacher stress management psychoeducation package, adapted from EBIs and including a half-day workshop for common stress management and a half-day for burnout management, and three follow-up group support sessions) will be tested to insure user-centeredness. we will recruit 4 study schools and applying factorial design to test the effect of each component (1 Common Stress management; 1 Burnout Stress management; 1 Combined Common and Burnout Stress management; 1 control; with ~15 teachers in each condition). Both groups' will also receive 3 post-workshop group support sessions. We will compare pre-post differences on teacher stress management and mental health using a mixed-methods data collection.

• To implement PD/PDT using a scalable approach, we will formalize partnership with the Ugandan Ministry of Education (MOE), Ministry of Health (MOH), academic medical center, and Teacher Training Colleges (TTCs) stakeholders in Year 1. The partnership and intervention implementation team will receive training from NYU PD trainers, and implement PD/PDT in Years 2-4.

• To study effectiveness-implementation aims (Aim 1-3), a cRCT will be conducted. Public primary schools from Kampala/urban and Hoima/ rural will be recruited. A stratified-block randomization procedure will be applied to ensure approximately similar characteristics across geographic regions and three intervention conditions (PD, PDT, and control). Teachers from the PD will receive a 3-day training, and teachers from the PDT will receive a 4-day training. Both intervention groups will receive 8 group-coaching sessions (with teachers from their own school). Teachers from the control schools will receive child mental health promotion materials. They will receive T-Wellness in Year 4 after the evaluation study is completed. Given the large numbers of students in schools, research staff will randomly select 10% of students and families from each school for participation in the evaluation study. A total of 1,980 families (parent-child pairs) from 36 schools (averaging 55 families/per school) will participate in the evaluation study. Effectiveness outcomes will be assessed at 3 time points over 18 months (baseline/T1, post-PD or PDT, 5-6 month/T2, and 16-18-month follow-up/T3). Objective observation, implementers, school staff, parent, and child report data (quantitative and qualitative) will be gathered.

• To study underlying mechanisms, we will use the evaluation data describe above to examine whether intervention effects on children's mental health outcomes is mediated through improvement on teachers' EBI practices (primary) and teacher stress coping. To study moderation mechanisms, geographic region, fidelity (including adherence, quality of program implementation, engagement, exposure) and other implementation contextual factors (i.e., EBI fidelity, school climate), guided by the Consolidated Framework for Implementation Research, will be studied.

• Identifiers will be removed from the identifiable survey and field notes. Data may be used for future research studies or shared with other researchers and we will not request additional informed consent from you to use these specimens as we have noted here.

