#### **Strategies for Ensuring a diverse, representative sample:**

For teacher sample, all primary school teachers are eligible to participate. No one will be excluded. For families, they will be randomly selected from student lists provided by schools/teachers. Only 10% families will be selected for the evaluation study. Therefore, it is expected that our teacher and family recruitment samples will be representative.

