#### **Potential recruitment/enrollment challenges and strategies for overcoming shortfalls:**

For school personnel recruitment, we anticipate that most teachers (>90%) will sign up for the study based on our prior experience. However, we anticipate some teachers will be on maternity leave, sick leave, or transferred to different schools during the study period. For those teachers, we will work with principals to determine alternative approaches to contact these teachers to gather data. A phone interview may be applied if such contact option is appropriate.

For families, we anticipate parents with low-literacy or struggling with poverty related stressors might be difficult to reach. If the situation happens, we will reach out to teachers and PTA for assistance in family recruitment and engagement. We will also apply strategies that we have learned from our previous studies, including sending home a reminder note to parent with students; calling parents; carrying out parent interview through home visits or phone calls.

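### At the stated averages, the 10% draw selects exactly the 1,980 families said to participate, leaving no margin for refusal, non-contact or ineligibility

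*Combined protocol and SAP*

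**What the plan says.** Section 4.4, in the paragraph on families under recruitment sources, gives the inputs: "Ugandan primary schools have on average about 550 students", and "research staff will randomly select 10% of students and families from each school based on student lists provided by teachers". Consent comes after the draw: "Targeted parents will be invited to consent for interviews, for teachers to complete ratings on their child's behavior".

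The fraction is repeated in two other places. Section 4.1 has "About 10% families will be randomly selected from the student lists". The part of Section 4.4 on a representative sample has "Only 10% families will be selected for the evaluation study".

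The resulting size is presented as enrolment. The description of procedures in the Protocol Summary states: "A total of 1,980 families (parent-child pairs) from 36 schools (averaging 55 families/per school) will participate in the evaluation study". The Methodology row of the same summary gives 1,980 pairs as the number to be recruited, Section 4.6 gives 1,980 as the number there will be, and the timeline table in Section 6.1 plans family data collection on 990 per cohort.

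On possible losses, Section 11.3 gives parents the right to refuse or withdraw, and Section 4.4 says "we anticipate parents with low-literacy or struggling with poverty related stressors might be difficult to reach". The response described there is more outreach: help from teachers and the PTA, reminder notes, calls and home visits. Schools that fall short of expected numbers are to be flagged for further action, which is not specified.

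**The concern.** One number does two jobs. It is the count of families drawn from the lists, and it is also the count of families who take part. Between the two lie contact, caregiver eligibility and voluntary consent, and each can only reduce the count.

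Three things are at stake. First, the stated child sample is larger than the rule can be expected to yield, and schools are monitored against expected enrolment numbers that share this base. Second, the claim that the family sample will be representative rests on random selection; with no replacement rule set in advance, a school that falls short may be topped up informally or left with a self-selected subset. Third, enrolment effort may not be the same in every arm. Teachers introduce the study to parents, and the PTA is to help reach difficult families, but Section 4.4 says control schools will have no identified PTA member. The documents do not show that consent will differ by arm, but without counts of approaches and consents by arm nobody could tell.

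**Working it through.** **Inputs from the documents.** About 550 pupils per school and a 10% draw (Section 4.4); "36 schools (12 receiving PD, 12 receive PDT, and 12 control"), that is, 12 schools per arm (Protocol Summary); 1,980 pairs, averaging 55 per school (Protocol Summary).

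**Inputs assumed.** The documents give no family consent rate, so 90%, 80% and 70% are used. Section 4.4's figure of more than 90% sign-up is for teachers and is not used for families. ICCs of 0.02 and 0.05 are also assumptions.

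**Step 1: reproduce the plan's figure.** 0.10 × 550 = 55 families per school, and 55 × 36 = 1,980. This matches the stated size exactly, with nothing left over.

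**Step 2: expected enrolment.** Enrolled = 1,980 × c, where c is the consent rate. Draws needed per school to enrol 55 = 55 / c. Mean school size at which a 10% draw would still enrol 1,980 = 550 / c.

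| Consent c | Pairs enrolled | Per school | Draws per school for 55 | Extra draws | Mean school size needed |
|---|---|---|---|---|---|
| 90% | 1,782 | 49.5 | 61.1 | about 6 | about 611 |
| 80% | 1,584 | 44.0 | 68.8 | about 14 | about 688 |
| 70% | 1,386 | 38.5 | 78.6 | about 24 | about 786 |

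The shortfalls are 198, 396 and 594 pairs.

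**Step 3: effect on precision.** For two arms of 12 schools with m pairs per school, two-sided 5% and 80% power, no baseline adjustment, and 36 − 3 = 33 degrees of freedom:

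detectable effect (SD) = (t₀.₉₇₅,₃₃ + t₀.₈₀,₃₃) × √{2[1 + (m − 1)ICC] / (12m)}, with t₀.₉₇₅,₃₃ + t₀.₈₀,₃₃ = 2.035 + 0.853 = 2.887 (unrounded sum).

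Example, m = 55 and ICC 0.05: 1 + 54 × 0.05 = 3.70; √(2 × 3.70 / 660) = 0.1059; × 2.887 = 0.306.

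| Pairs per school | ICC 0.02 | ICC 0.05 |
|---|---|---|
| 55 (full consent) | 0.229 | 0.306 |
| 49.5 (90%) | 0.235 | 0.310 |
| 44 (80%) | 0.242 | 0.315 |
| 38.5 (70%) | 0.251 | 0.322 |

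At ICC 0.05 the detectable effect rises by about 1% at 90% consent (0.310 / 0.306) and about 5% at 70% (0.322 / 0.306). At ICC 0.02 the rises are about 3% and 10%.

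**The case against.** The strongest reply is that the inputs are rough planning values. The 550 is an approximate average for Ugandan primary schools in general, the 36 study schools were still to be chosen with the Ministry of Education, and Section 4.1 gives the fraction only approximately. Study schools averaging about 611 pupils would enrol 1,980 at 90% consent. This stands: a reader might infer that the target can be met only if every family consents, and the documents support that only at the stated averages.

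A reader might also infer that the protocol itself predicts incomplete consent. It does not say so. The remark about hard-to-reach parents is conditional, concerns contact rather than refusal, and comes with remedies; Section 4.4 also cites engagement strategies intended to secure high enrolment. Less than full consent is a fair inference from voluntary participation, but it is an inference.

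Nor do the documents rule out replacement. The further action for flagged schools is left open, so the accurate statement is that none is described.

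Finally, the statistical consequence is slight, and Section 9 quotes no power or detectable effect based on 1,980 that would need correcting. That also stands, and it limits the weight of the point. None of these replies supplies the missing allowance.

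**Conclusion.** The point holds as an enrolment figure with no margin. At the stated averages, the number selected and the number stated to participate are the same 1,980, and nothing in the plan covers the losses between them. The shortfall would be 198 to 594 pairs at assumed consent of 90% to 70%.

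It does not show an underpowered trial, although a reader might infer one. With 12 schools per arm, the number of schools drives precision, and even 70% consent moves the detectable effect by only 0.016 SD at ICC 0.05 and 0.022 SD at ICC 0.02. These results depend on the assumed ICCs and consent rates and on an analysis without baseline adjustment.

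Two further extensions are not supported. One is that the yield is lower still because only Pre-Primary to Primary 4 pupils are eligible: the documents do not say which grades the 550 covers, so no figure can be given. The other is to combine this with loss to follow-up: 1,980 is stated as a participating number, not as completers at the last assessment, and attrition is a separate question.

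**What to change.** Either of two changes would settle it.

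1. Restate 1,980 as the number of families selected and invited wherever it now appears as recruited or participating (Protocol Summary, Section 4.6, and 990 per cohort in the timeline table), and give the expected number enrolled over a stated range of consent rates. This costs a sentence, matching edits and a slightly less favourable headline figure.

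2. Keep 1,980 as the enrolment target and replace the flat 10% in Sections 4.1 and 4.4 and the Protocol Summary with a randomly ordered list of eligible Pre-Primary to Primary 4 pupils in each school, approached in order until 55 families consent. At 90% to 70% consent this means about 6 to 24 extra approaches per school. It also fixes the replacement order in advance, which protects the representativeness claim.

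Under either option, record approaches and consents by school and arm, so that differential enrolment can be seen and reported.
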